### **8.1.5 Clinical Laboratory Evaluations**

A change in the value of a clinical laboratory investigation can represent an AE if the change is clinically relevant or if, during treatment with the investigational product, a shift of a parameter is observed from a normal value to an abnormal value, or a further worsening of an already abnormal value. When evaluating such changes, the extent of deviation from the reference range, the duration until return to the reference range, either while continuing treatment or after the end of treatment with the investigational product, and the range of variation of the respective parameter within its reference range, must be taken into consideration.

If, at the end of the treatment phase, there are abnormal clinical laboratory values which were not present at baseline, further clinical or laboratory investigations should be performed until the values return to within the reference range or until a plausible explanation (eg, concomitant disease) is found for the abnormal clinical laboratory values.

The Investigator should decide, based on the above criteria and the clinical condition of a subject, whether a change in a clinical laboratory parameter is clinically significant and therefore represents an AE.

### **8.1.6 Pregnancy**

All pregnancies are to be reported from the time informed consent is signed until the defined follow-up period stated in Section 7.1.3.

Any report of pregnancy for any female study participant must be reported within 24 hours to the Shire Pharmacovigilance Department using the Shire Pharmaceuticals Investigational and Marketed Products Pregnancy Report Form. The female study participant must be withdrawn from the study.

Every effort should be made to gather information regarding the pregnancy outcome and condition of the infant. It is the responsibility of the Investigator to obtain this information within 30 calendar days after the initial notification and approximately 30 calendar days post-partum.

Pregnancy complications such as spontaneous abortion/miscarriage or congenital abnormality are considered SAEs and must be reported using the Shire Pharmaceuticals Clinical Trial Serious Adverse Event Form. Note: An elective abortion is not considered an SAE.

In addition to the above, if the Investigator determines that the pregnancy meets serious criteria, it must be reported as an SAE using the Shire Pharmaceuticals Clinical Trial Serious Adverse Event Form as well as the Shire Pharmaceuticals Investigational and Marketed Products Pregnancy Report Form. The test date of the first positive serum/urine human chorionic gonadotropin test or ultrasound result will determine the pregnancy onset date.

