**Part 2b:** Subjects will begin 8 weeks of treatment with lanthanum carbonate. Lanthanum carbonate will be mixed with food and given 3 times a day. If the subject has only 2 meals a day the lanthanum carbonate dose will split equally across the 2 meals with a single dose not exceeding 1000mg. The starting total daily dose of lanthanum carbonate is 1500mg for all subjects. The total daily dose will be titrated 2-weekly, as appropriate, until the target serum phosphorus level is achieved, or until a maximum daily dose of 3000mg is reached. Once serum phosphorus control is achieved or the maximum dose is reached, the dose of lanthanum carbonate will be maintained until the end of the 8-week treatment period. All new subjects will be enrolled in Part 2b only under Version 6.0 of the protocol.

**Part 3:** Subjects who complete participation in Part 2 (2a or 2b) may continue to receive lanthanum carbonate for an additional 6 months (including subjects who participated in Part 2a, Treatment Period 1/calcium carbonate treatment arm, but who discontinued due to hypercalcemia). The dosage of lanthanum carbonate will be determined by the Investigator based on serum phosphate levels taken at each study visit up to a maximum dose of 3000mg/day.

**Safety Follow-up:** A safety follow-up telephone call will be made to all subjects or their parent/legally authorized representative (LAR) 7-14 days following the last dose. In the event of early discontinuation due to kidney transplantation, the safety follow-up call will be 30±7 days from the last dose.

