### **4.3 Reproductive Potential**

All females must have a negative serum beta human chorionic gonadotropin pregnancy test at Visit 1.0 and/or Visit 2.0. Females must abstain from sexual activity that could result in pregnancy or agree to use acceptable methods of contraception.

Condoms should be used with the following acceptable contraceptives:

- Intrauterine devices
- Hormonal contraceptives (oral, depot, patch, injectable, or vaginal ring).

Other acceptable contraception methods are:

- Double barrier methods (eg, condoms and diaphragms with spermicidal gel or foam).

Sexually active females should have been using an acceptable form of contraception for at least 4 weeks prior to enrollment. All females must be advised to use acceptable contraceptives throughout the study period and for 30 days following the last dose of investigational product. If hormonal contraceptives are used they should be administered according to the package insert. Females who are not currently sexually active must agree to use acceptable contraception, as defined above, if they become sexually active during the period of the study and 30 days following the last dose of investigational product.

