#### 5.2 Concomitant Treatment

Concomitant treatment taken between the dates of the first and last dose of investigational product, inclusive, must be listed on the appropriate CRF page.

Treatments not listed in [Table 4](#) above are considered allowable.

Subjects who require treatment with Vitamin D analogues should maintain a stable dose throughout the study unless modification is required due to hypercalcaemia as specified in Section 6.2.1. Vitamin D therapy including dose, unit, route, regimen, indication and dates of use, and the calcium concentration of the dialysate will also be recorded in the CRF.

Treatment with cinacalcet hydrochloride, or with compounds containing phosphate or magnesium, aluminum, or calcium that are used as a phosphate binder are prohibited during the study.

Contraceptives for females should be taken at least 4 weeks prior to enrollment and continued throughout the duration of the study and for 30 days following the last dose of investigational product.

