#### **7.1.3 Follow-up Period**

The safety follow-up call for this protocol is 7-14 days following last dose of investigational product ([Table 1](#) and [Table 3](#)). Subjects who discontinue due to kidney transplantation, will have their safety follow-up call after  $30 \pm 7$  days from the last dose.

The telephone call is initiated by the site staff to query for serious adverse events (SAEs), AEs, and concomitant treatments.

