### 7.2.3.6 Pregnancy Test

A serum pregnancy test is performed on all female subjects at Visit 1.0, and/or Visit 2.0, and at the final visit (Visit 3.5), or if pregnancy is suspected, or on withdrawal of the subject from the study (see [Table 1](#) and [Table 3](#)).

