**7.2.5 Volume of Blood to be Drawn From Each Subject**

**Table 5: Volume of Blood to be Drawn From Each Subject**

Assessment		Sample Volume (mL)	Number of Samples	Maximum Total Volume (mL)
Pharmacokinetic samples		1.0 a	12	12.0
Safety	Biochemistry with $\beta$ -HCG a	4.0	4	16.0
	Hematology	0.5	2	1.0
	Biochemical bone markers	3.0	4	12.0
	Centrally confirmed phosphate b	0.1-0.7 c	2	1.4
Total mL				42.4

HCG=human chorionic gonadotropin

a  $\beta$ -HCG testing for all female subjects will be analyzed from the biochemistry samples so no additional blood volume is required

b Only for those subjects who require confirmation of their phosphate levels from the central laboratory, during the washout periods

c Volume will vary according to country

In the originally proposed study, it was expected that approximately 41.0mL of blood will be taken from all subjects, regardless of sex; a maximum of 42.4mL of blood will be taken from those subjects who require confirmation of their phosphate levels during both washouts in Part 2 (41.7mL if they only require confirmation during 1 of the washouts).

Under Version 6.0 of the protocol, subjects will enter Part 2b, after screening at Visit 1.0/Week 0 for this part, for 8 weeks of lanthanum carbonate treatment only. They will undergo assessments for Part 2b and 3 as presented in [Table 3](#). It is expected that approximately 34mL of blood will be taken from all subjects, regardless of sex.

Note: The above amount of blood to be taken for each assessment is an estimate. The amount of blood to be taken may vary according to the instructions provided by the manufacturer or laboratory for an individual assessment. However, the total volume drawn over the course of the study should be approximately 41.0mL (maximum of 42.4mL). When more than 1 blood

assessment is to be done at the time point/period, if they require the same type of tube, the assessments may be combined.

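### Except after kidney transplantation, mandatory pregnancy reporting ends at the 7-14 day follow-up, although the protocol requires contraception for 30 days after the last dose

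*Protocol*

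**What the plan says.** **Reporting window.** Section 8.1.6 of the protocol states: "All pregnancies are to be reported from the time informed consent is signed until the defined follow-up period stated in Section 7.1.3". Section 7.1.3 defines that follow-up: "The safety follow-up call for this protocol is 7-14 days following last dose of investigational product". The exception appears there and in the synopsis: "In the event of early discontinuation due to kidney transplantation, the safety follow-up call will be 30±7 days from the last dose". Section 7.1.3 says site staff use the call to query SAEs, AEs and concomitant treatments. Pregnancy is not listed.

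**Contraception window.** Section 4.3 states: "All females must be advised to use acceptable contraceptives throughout the study period and for 30 days following the last dose of investigational product". Section 5.2 repeats the period, with contraceptives to be "continued throughout the duration of the study and for 30 days following the last dose of investigational product".

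**Testing.** Section 7.2.3.6 states: "A serum pregnancy test is performed on all female subjects at Visit 1.0, and/or Visit 2.0, and at the final visit (Visit 3.5"), and adds unscheduled tests "or if pregnancy is suspected, or on withdrawal of the subject from the study". Tables 1 and 3 agree on the scheduled tests: baseline and Visit 3.5, none between. Footnote c to both tables brings the Visit 3.5 assessments forward to early discontinuation but exempts subjects after a transplant. Table 5 has a row of four samples that combines biochemistry with β-HCG. Its footnote says that β-HCG "testing for all female subjects will be analyzed from the biochemistry samples so no additional blood volume is required".

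**The concern.** The protocol asks females aged 10 to under 18 to avoid pregnancy for 30 days after dosing, yet for most of them it stops requiring pregnancy reports about one to two weeks after dosing. A pregnancy that begins in the remaining days is one the protocol set out to prevent but does not require anyone to report.

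The likely route is a conception near or shortly after the last dose. The Visit 3.5 test cannot detect a conception that follows it and may miss one just before it. The call follows 7-14 days after the last dose and has no stated pregnancy question. If the pregnancy is recognised after the call, the reporting window has closed. Section 8.1.6 times the collection of pregnancy and infant outcome from the initial notification, so an unreported pregnancy also loses its outcome. Protocol Section 9.13 says that the focus of the study has moved to safety in a population with little information, so this loss is worth avoiding.

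**Working it through.** The documents give no figure on this point to reproduce. The check is day arithmetic on their own windows, followed by a comparison of passages.

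**Inputs**
- Contraception period C = 30 days after the last dose (Sections 4.3 and 5.2).
- Follow-up day F = 7 to 14 (Section 7.1.3, general rule).
- Follow-up day F = 30 − 7 = 23 to 30 + 7 = 37 (Section 7.1.3 and synopsis, transplant discontinuations).

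**Formula:** days outside mandatory reporting = max(0, C − F).

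| Group | Latest call | Earliest call |
|---|---|---|
| General rule | 30 − 14 = 16 days (16/30 = 53%) | 30 − 7 = 23 days (23/30 = 77%) |
| Transplant discontinuation | 30 − 37 < 0, so 0 days | 30 − 23 = 7 days |

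With reporting to day 30, the gap is 30 − 30 = 0 days in both groups.

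**Could another rule close the gap?**
- Section 8.1.6 also requires any report of pregnancy to reach the sponsor within 24 hours. That sets the speed of a report once someone makes it. It obliges nobody to ask, and it follows a sentence that closes the window.
- Section 8.2.4 keeps reporting open after the study, but only for SAEs judged related. Section 8.1.6 classes pregnancy complications as SAEs, so a complication judged related would qualify. An uncomplicated pregnancy would not.

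**Two further mismatches**
- *Table 5 against the schedules.* Table 1 shows biochemistry at baseline and at Visits 2.4, 2.8 and 3.5, which makes four draws. Only the baseline and Visit 3.5 draws carry a pregnancy test. Table 3 has three biochemistry draws (Visits 1.0, 2.4 and 3.5) and two pregnancy tests (Visits 1.0 and 3.5). The row in Table 5 attaches β-HCG to all four draws.
- *Test on withdrawal.* Section 7.2.3.6 requires a pregnancy test at withdrawal. Footnote c to Tables 1 and 3 exempts post-transplant subjects from the Visit 3.5 assessments, which include that test. Section 4.4.1 makes a transplant a reason for removal from the study, so both rules apply to the same subject.

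**The case against.** **The two windows may differ on purpose.** Sections 4.3 and 5.2 give no reason for the 30 days and do not mention residual exposure or fetal risk. A contraception period and a reporting period can legitimately differ. This stands as a limit: the 30 days should not be called an established risk period, and 53-77% is a share of calendar days, not of pregnancies lost. It does not remove the mismatch, because the protocol gives no reason for collecting less than the period it asks families to cover.

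**Pregnancies on treatment are not left unwatched.** A reader might infer from the absence of a scheduled test between baseline and Visit 3.5 that pregnancies go undetected for most of the study. The documents do not support that. Tests are required on suspicion and on withdrawal, and Visit 3.5 assessments move to early discontinuation except after transplant. Visits are two-weekly and then monthly, with a general health question at each. For a continuing pregnancy conceived on treatment, sparse testing mainly delays detection.

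**Washout weeks do not extend treatment.** A reader might also add washouts to Weeks 32 and 40 and describe on-treatment gaps of 32 + 3 = 35 or 40 + 3 + 3 = 46 weeks. Washout is time off study binder, and W1 precedes the first Part 2 dose. Sections 7.1.1.2 and 7.1.1.3 also want pregnancy results from samples within 7 days of planned enrolment. How that rule applies to a subject entering washout is not fully clear, but the longer figures cannot be called time on treatment. Part 2a is closed to new subjects under Version 6.0.

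**Table 5 schedules nothing.** This is correct. It is a blood-volume table, and its footnote says only that no extra blood is needed. The row label can mislead, but it does not show that mid-study tests were intended.

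**Conclusion.** The mismatch is real and rests on the protocol's own wording. For all subjects except transplant discontinuations, 16-23 of the 30 contraception days fall after mandatory pregnancy reporting ends. For transplant discontinuations the shortfall is 0-7 days. What can be lost is a pregnancy conceived late in or just after treatment and recognised after the call, together with its outcome.

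The conclusion assumes that Section 8.1.6 is applied as written and that the call covers only the topics listed in Section 7.1.3. The number of pregnancies affected cannot be estimated from the documents. The point concerns completeness of safety reporting and does not touch the efficacy analysis. It merits correction because following the rule as written would leave late-recognised pregnancies uncollected. The Table 5 label and the transplant exemption are minor inconsistencies. Neither supports a claim about how often tests should be done.

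**What to change.** 1. Reconcile Section 8.1.6 with Sections 4.3 and 5.2 by running pregnancy reporting to 30 days after the last dose. Where the transplant call falls after day 30, keep the later date so that nothing now covered is lost.
2. Add pregnancy to the topics of the follow-up call in Section 7.1.3. At that call, tell female subjects or their parent/LAR to report a pregnancy recognised later if conception fell within the 30 days.
3. Reconcile the β-HCG row of Table 5 with Tables 1 and 3 and Section 7.2.3.6, so that it is clear which samples carry a pregnancy test.
4. Reconcile the test on withdrawal in Section 7.2.3.6 with the post-transplant exemption in footnote c to Tables 1 and 3.

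Items 3 and 4 ask for consistent text and do not propose a testing schedule. The cost is minor wording, one added question and instruction at an existing call, and a few late reports to process. No visit or blood draw is added. Capture after the call would still depend on the family making contact.

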### **8.1.7 Abuse, Misuse, Overdose, and Medication Error**

Abuse, misuse, overdose, or medication error (as defined below) must be reported to the Sponsor according to the SAE reporting procedure whether or not they result in an AE/SAE as described

in Section 8.2. Note: The 24 hours reporting requirement for SAEs does not apply to reports of abuse, misuse, overdose, or medication errors unless these result in an SAE.

The categories below are not mutually exclusive; the event can meet more than 1 category.

- **Abuse** – Persistent or sporadic intentional intake of investigational product when used for a non-medical purpose (eg, to alter one’s state of consciousness or get high) in a manner that may be detrimental to the individual and/or society.
- **Misuse** – Intentional use of investigational product other than as directed or indicated at any dose (Note: this includes a situation where the investigational product is not used as directed at the dose prescribed by the protocol).
- **Overdose** – Intentional or unintentional intake of a dose of an investigational product exceeding a pre-specified total daily dose of 3000mg of lanthanum and 6500mg of calcium.
- **Medication Error** – An error made in prescribing, dispensing, administration, and/or use of an investigational product. For studies, medication errors are reportable to the Sponsor only as defined below.

Cases of subjects missing doses of product are not considered reportable as medication errors. Medication errors should be collected/reported for all products under investigation. The administration and/or use of the unassigned treatment is always reportable as a medication error. The administration and/or use of an expired product should be considered as a reportable medication error.

All investigational product provided to pediatric subjects should be supervised by the parent/LAR/caregiver.

## 8.2 Serious Adverse Event Procedures

### 8.2.1 Reference Safety Information

The reference for safety information for lanthanum carbonate for this study is the current SPD405 IB which the Sponsor has provided under separate cover to all Investigators, and the Summary of Product Characteristics.

The reference for safety information for the comparator/reference product in this study (calcium carbonate) is the Summary of Product Characteristics which the Sponsor has provided under separate cover to all Investigators.

### 8.2.2 Reporting Procedures

All initial and follow-up SAE reports must be reported by the Investigator to the Shire Pharmacovigilance Department within 24 hours of the first awareness of the event. Note: The 24 hours reporting requirement for SAEs does not apply to reports of abuse, misuse, overdose, or medication errors (see Section 8.1.7) unless they result in an SAE.

The Investigator must complete, sign, and date the Shire Pharmaceuticals Clinical Trial Serious Adverse Event Form and verify the accuracy of the information recorded on the form with the

corresponding source documents (Note: Source documents are not to be sent unless requested) and fax or e-mail the form to the Shire Pharmacovigilance Department.

### 8.2.3 Serious Adverse Event Definition

A *Serious Adverse Event (SAE)* is any untoward medical occurrence (whether considered to be related to investigational product or not) that at any dose:

- Results in death
- Is life-threatening  
*NOTE:* The term ‘life-threatening’ in the definition of ‘serious’ refers to an event in which the subject was at risk of death at the time of the event; it does not refer to an event which hypothetically might have caused death if it was more severe.
- Requires inpatient hospitalization or prolongation of existing hospitalization
- Results in persistent or significant disability/incapacity
- Is a congenital abnormality/birth defect
- Is an important medical event; Note: Important medical events that may not result in death, be life-threatening, or require hospitalization may be considered an SAE when, based upon appropriate medical judgment, they may jeopardise the subject and may require medical or surgical intervention to prevent 1 of the outcomes listed in this definition. Examples of such medical events include allergic bronchospasm requiring intensive treatment in an emergency room or at home; blood dyscrasias or convulsions that do not result in inpatient hospitalization; or the development of drug dependency or drug abuse.

Hospitalizations, which are the result of elective or previously scheduled surgery for pre-existing conditions, which have not worsened after initiation of treatment, should not be classified as SAEs. For example, an admission for a previously scheduled ventral hernia repair would not be classified as an SAE.

However, complication(s) resulting from a hospitalization for an elective or previously scheduled surgery that meets serious criteria must be reported as SAE(s).

### 8.2.4 Serious Adverse Event Collection Timeframe

All SAEs (regardless of relationship to study) are collected from the time the subject signs informed consent until the defined follow-up period stated in Section 7.1.3, and must be reported to the Shire Pharmacovigilance Department within 24 hours of the first awareness of the event.

In addition, any SAE(s) considered “related” to the investigational product and discovered by the Investigator at any interval after the study has completed must be reported to the Shire Pharmacovigilance Department within 24 hours of the first awareness of the event.

### 8.2.5 Serious Adverse Event Onset and Resolution Dates

The onset date of the SAE is defined as the date the event meets serious criteria. The resolution date is the date the event no longer meets serious criteria, the date the symptoms resolve, or the

event is considered chronic. In the case of hospitalizations, the hospital admission and discharge dates are considered the onset and resolution dates, respectively.

In addition, any signs or symptoms experienced by the subject prior to study entry or leading up to the onset date of the SAE or following the resolution date of the SAE, must be recorded as an AE, if appropriate.

